I have read and agree to the protocol, as detailed in this document. I am aware of my responsibilities as an Investigator under the International Conference on Harmonisation Guideline (ICH) for Good Clinical Practice (GCP), the Declaration of Helsinki, all local, regional, and national regulatory requirements (including the Code of Federal Regulations [CFR] Title 21 for US Investigators), requirements of the applicable Institutional Review Board/Independent Ethics Committee, and the clinical trial protocol. I agree to conduct the trial according to these regulations and guidelines, to appropriately direct and assist the staff under my control that will be involved in the trial, and ensure that all staff members are aware of their clinical trial responsibilities.

Investigator Name:

Name of Institution/Site:

Signature:

Date:

PROTOCOL SYNOPSIS

NAME OF INVESTIGATIONAL PRODUCT: KZR-616
NAME OF ACTIVE INGREDIENT: KZR-616
CLINICAL CONDITION(S)/INDICATION(S) 
• Polymyositis (PM)• Dermatomyositis (DM)
PROTOCOL NUMBER: KZR-616-003E
PROTOCOL TITLE: An Open-label Extension to the Phase 2 Randomized, Double-blind, Placebo-controlled, Crossover Multicenter Study to Evaluate the Safety and Efficacy of KZR-616 in the Treatment of Patients with Active Polymyositis or Dermatomyositis
SHORT TITLE: An Open-label Extension to Study KZR-616-003
STUDY PHASE: Phase 2
STUDY OBJECTIVES: Efficacy: To evaluate the long-term efficacy of KZR-616 in patients with PM or DM. Safety: To evaluate the long-term safety and tolerability of KZR-616 in patients with PM or DM.
STUDY DESIGN: This is an open-label study to evaluate the long-term efficacy and safety of KZR-616 in patients with active PM or DM who completed the double-blind treatment period of Study KZR-616-003, up to and including the Week 32 Visit, prior to the first dose of open-label KZR-616. Patients will be evaluated for eligibility according to the entry criteria at, or within 8 weeks after, the Week 32 Visit (ie, the End of Treatment [EOT] Visit [Visit 34]) of Study KZR-616-003. Informed consent may be signed prior to the Week 32 Visit of Study KZR-616-003, and must be signed prior to any study-related activity in KZR-616-003E. For patients who are eligible and willing to enroll in the open-label extension study, the KZR-616-003 Week 32 Visit may also serve as Visit 1 (Day 1) for the open-label extension study. Assessments at this visit performed as part of Study KZR-616-003 will be used as baseline values for the extension study; therefore, these assessments must be performed prior to the first dose of open-label KZR-616. All patients will receive a subcutaneous (SC) injection of 30 mg KZR-616 at Visit 1 (Day 1), followed by weekly SC injections of 45 mg KZR-616 up to a maximum of 96 weeks. Study drug administration will end for all patients in Study KZR-616-003E when the last patient enrolled has completed 48 weeks of dosing. Patients will have a final follow-up visit 12 weeks after their last dose of KZR-616 (End of Study [EOS] Visit), for a maximum potential length of participation of 108 weeks. On-site study visits will occur at Weeks 12, 24, 36, 48, 60, 72, 84, and 96 (EOT Visit), and the EOS Visit. At these visits, safety and efficacy assessments will be performed according to the Schedule of Assessments (Table 1). While these visits are mandatory, in recognition of constraints imposed by the SARS-CoV-2 pandemic, sites may elect to use a combination of telemedicine (as permitted by their institutions) and/or home health providers, including at-home administration of KZR-616. All other study visits may occur either at the site or at patients' homes via home health providers (Table 2). If necessary, samples for clinical laboratory assessments will be collected by home health providers and sent to the laboratory. For at-home KZR-616 administration, doses may be administered by home health providers or, for patients deemed appropriate by the Investigator, by the patient or caregiver following appropriate instruction (see Section 5.4).

ENDPOINTS:

Efficacy Endpoints:

- Mean change in TIS over time for all patients, for patients with DM only, for patients with PM only, and for patients with a myositis-associated antibody or myositis-specific antibody at the Screening Visit of Study KZR-616-003
- Proportion of patients by TIS response (minimal response = TIS \geq 20, moderate response = TIS \geq 40, major response = TIS \geq 60)
- Proportion of patients meeting International Myositis Assessment and Clinical Studies Group (IMACS) definition of improvement (DOI) over time for patients with baseline core set measures as ascertained at the beginning of KZR-616-003
- Mean change and mean percentage change over time in the IMACS individual core set activity measures (CSAMs) and core set damage measures (CSDMs), stratified by all patients and patients with myositis-associated or myositis-specific antibody at the Screening Visit of Study KZR-616-003
- Mean change over time in the Cutaneous Dermatomyositis Disease Area and Severity Index (CDASI) for all patients with DM, and for patients with DM who have active skin manifestations at baseline of Study KZR-616-003E
- Mean change over time in the Myositis Damage Index (MDI)
- Mean change over time in muscle enzymes
- Change in proportion and dose of corticosteroid and non-corticosteroid immunosuppressants during Study KZR-616-003E for all patients, and for patients taking corticosteroids or non-corticosteroid immunosuppressants at baseline of Study KZR-616-003E
- Percentage of patients requiring additional medication for myositis treatment during Study KZR-616-003E
- Mean change over time in the EuroQol 5-dimension 5-level (EQ-5D-5L)
- Additional exploratory endpoints (Physician Global Impression of Change [MDGIC], Functional Index-2 [FI-2], Patient Global Impression of Change [PGIC], and Peak Pruritis Numerical Rating Scale [NRS]) will be assessed at multiple time points

Safety Endpoints:

- Incidence, nature, and severity of adverse events (AEs) and serious adverse events (SAEs)
- Incidence of AEs leading to KZR-616 discontinuation
- Changes in standard laboratory parameters and vital signs

Exploratory Endpoints:

- Relationships between clinical efficacy, clinical safety, and various biomarker endpoints including changes in circulating cytokine and whole blood gene expression
- Corticosteroid-free TIS response by visit (corticosteroid-free is defined as corticosteroid fully tapered off for \geq 12 weeks [3 months] prior to a visit; minimal response = TIS \geq 20, moderate response = TIS \geq 40, major response = TIS \geq 60)

INVESTIGATIONAL PRODUCT(S), DOSE, AND MODE OF ADMINISTRATION:

Active Product:

Investigational Medicinal Product: KZR-616 is supplied as a refrigerated lyophilized drug product in single-use borosilicate glass vials packaged in multi-vial cartons. For patients eligible for at-home administration by the patient or caregiver, a premeasured, pre-filled syringe (PFS) containing sterile water for injection (WFI), a needless vial adaptor system, and additional clinical supplies needed for reconstitution will also be provided.

Dose and Dose Frequency: KZR-616 will be administered by SC injection once weekly. The first injection will be a 30-mg dose, and subsequent injections will be a 45-mg dose.

Control/Comparator:

This is an open-label study with no control or comparator.

PATIENT SELECTION:

Targeted Number of Patients: Up to 24 patients

Planned Number of Sites: Up to 24 sites

Inclusion Criteria:

1. Must have successfully completed Study KZR-616-003 through Week 32, including the Week 32 Visit assessments, be willing and able to provide written informed consent prior to any study-related procedures, and be willing and able to comply with study requirements.
2. Women of childbearing potential (WOCBP) must have a negative urine or serum pregnancy test prior to the first dose of KZR-616 in Study KZR-616-003E, and must agree to continue to use a highly effective method of birth control until completion of the study (or 30 days following the last dose of KZR-616 in case of early withdrawal). Women of childbearing potential are defined as postpubescent female patients, unless the patient is postmenopausal (defined by amenorrhea for at least 2 years or amenorrhea for at least 1 year with confirmatory follicle stimulating hormone [FSH] level in the postmenopausal range, as documented historically or measured by the central or local laboratory and if patient is not on supplementary hormonal therapy) or surgically sterile (ie, tubal ligation, hysterectomy, bilateral salpingoophorectomy).
3. Male patients must continue to use an effective contraception method (eg, condom with spermicide) for 1 week following their last dose of KZR-616 or be congenitally or surgically sterile (eg, vasectomy with documented confirmation of post-surgical aspermia).

Exclusion Criteria:

1. Have clinical evidence of significant unstable or uncontrolled diseases other than the disease under study (eg, cardiac [including congestive heart failure, hypertension, angina, or myocardial infarction], pulmonary [including pulmonary hypertension or interstitial lung disease], hematologic, gastrointestinal, endocrinologic, hepatic, renal, neurological, or infectious disease, any ongoing SAE(s), or AE(s) \geq Grade 3 by National Cancer Institute Common Terminology Criteria for Adverse Events [NCI-CTCAE]) that, in the opinion of the Investigator or Sponsor/designee, could confound the results of the study, put the patient at undue risk, or interfere with protocol adherence.
2. Has participated in any clinical study other than KZR-616-003 between the Week 32 Visit of Study KZR-616-003 and the first study visit of KZR-616-003E, if they are not on the same calendar day.
3. Are females who are breastfeeding or who plan to become pregnant during the study, or who are actively trying to conceive at the time of signing of the informed consent form (ICF).
4. Have hypersensitivity to KZR-616 or any of its excipients.

STATISTICAL ANALYSIS:

This study is descriptive in nature, and no formal hypothesis testing will be performed. No formal statistical sample size estimation has been performed, since the number of patients in this study is determined by the number of patients who completed Study KZR-616-003 and enrolled in this study.

Analysis Sets:

Full Analysis Set (FAS): The FAS for summaries of efficacy endpoints will include all patients who receive KZR-616 in this study and have baseline and any post baseline data. All observed data will be included in the statistical summaries. No missing data will be imputed except as pre-defined in the statistical analysis plan (SAP).

Per Protocol (PP): A PP population may be used to analyze select efficacy endpoints, and will be based on KZR-616 exposure (time on treatment) and protocol deviations. The decision to summarize a PP population will be made prior to database lock.

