1.5. Rationale for Study Endpoints

The Myositis Response Criteria are recommended for use as primary endpoints in myositis therapeutic trials. The criteria use core set activity measures (CSAMs) from the International Myositis Assessment and Clinical Studies Group (IMACS). By combining the absolute percentage change in these 6 core set measures (each with varying weights), a Total Improvement Score (TIS), ranging from 0 to 100, is obtained. The IMACS CSAMs consist of:

- Manual Muscle Testing-8 Muscle Groups (MMT-8)
- Physician Global Assessment (MDGA)
- Patient Global Assessments of Disease Activity (PtGADA)
- Health Assessment Questionnaire-Disability Index (HAQ-DI)
- Muscle enzymes (clinical laboratory assessments): CK, aldolase, lactate dehydrogenase (LDH), alanine aminotransferase (ALT), and aspartate aminotransferase (AST)
- Myositis Disease Activity Assessment Tool (MDAAT, 2005 version)

In addition, IMACS has defined the following core set damage measures (CSDMs):

- Myositis Damage Index (MDI)
- Patient Global Assessment of Disease Damage (PtGADD)

Mean change from start to end of KZR-616 treatment was the primary efficacy endpoint for Study KZR-616-003, and secondary and exploratory endpoints utilized the CSAMs and CSDMs, along with other measures of function and outcomes. To determine long-term efficacy in the same patient population, many of the endpoints used in Study KZR-616-003 will also be used in this study with consideration for treatment periods (see [Section 10](#)).

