2.2. Study Endpoints

2.2.1. Efficacy Endpoints

- Mean change in TIS over time for all patients, for patients with DM only, for patients with PM only, and for patients with a myositis-associated antibody or myositis-specific antibody at the Screening Visit of Study KZR-616-003
- Proportion of patients by TIS response (minimal response = TIS \geq 20, moderate response = TIS \geq 40, major response = TIS \geq 60)
- Proportion of patients meeting IMACS definition of improvement (DOI) over time for patients with baseline core set measures as ascertained at the beginning of KZR-616-003
- Mean change and mean percentage change over time in the IMACS individual CSAMs and CSDMs, stratified by all patients and patients with myositis-associated or myositis-specific antibody at the Screening Visit of Study KZR-616-003
- Mean change over time in the Cutaneous Dermatomyositis Disease Area and Severity Index (CDASI) for all patients with DM, and for patients with DM who have active skin manifestations at baseline of Study KZR-616-003E
- Mean change over time in the MDI
- Mean change over time in muscle enzymes
- Change in proportion and dose of corticosteroid and non-corticosteroid immunosuppressants during Study KZR-616-003E for all patients, and for patients taking corticosteroids or non-corticosteroid immunosuppressants at baseline of Study KZR-616-003E
- Percentage of patients requiring additional medication for myositis treatment during Study KZR-616-003E
- Mean change over time in the EuroQol 5-dimension 5-level (EQ-5D-5L)
- Additional exploratory endpoints (Physician Global Impression of Change [MDGIC], Functional Index-2 [FI-2], Patient Global Impression of Change [PGIC], and Peak Pruritis Numerical Rating Scale [NRS]) will be assessed at multiple time points

As KZR-616-003E is an open-label extension study, additional exploratory endpoints may be conducted, and will be described in the final statistical analysis plan (SAP). Efficacy endpoints may include treatment periods that include data from Study KZR-616-003 based on treatment sequence in that study. See [Section 10](#) for additional details of statistical analyses.

All endpoints, except where noted, will include analyses of all patients, those with DM only, and those with PM only.

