3. STUDY DESIGN

3.1. Type and Design of Study

This is an open-label study to evaluate the long-term efficacy and safety of KZR-616 in patients with active PM or DM who completed the double-blind treatment period of Study KZR-616-003, up to and including the Week 32 Visit, prior to the first dose of open-label KZR-616.

The study design schema is presented in [Figure 1](#).

Patients will be evaluated for eligibility according to the entry criteria (see [Section 4](#)) at, or within 8 weeks after, the Week 32 Visit (ie, the End of Treatment [EOT] Visit [Visit 34]) of Study KZR-616-003. Informed consent may be signed prior to the Week 32 Visit of Study KZR-616-003, and must be signed prior to any study-related activity in KZR-616-003E. For patients who are eligible and willing to enroll in the open-label extension study, the KZR-616-003 Week 32 Visit may also serve as Visit 1 (Day 1) for the open-label extension study. Assessments at this visit performed as part of Study KZR-616-003 will be used as baseline values for the extension study; therefore, these assessments must be performed prior to the first dose of open-label KZR-616 (see [Figure 1](#)).

[figure not shown]
All patients will receive a SC injection of 30 mg KZR-616 at Visit 1 (Day 1), followed by weekly SC injections of 45 mg KZR-616 up to a maximum of 96 weeks. Study drug administration will end for all patients in Study KZR-616-003E when the last patient enrolled has completed 48 weeks of dosing. Patients will have a final follow-up visit 12 weeks after their last dose of KZR-616 (End of Study [EOS] Visit), for a maximum potential length of participation of 108 weeks.

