Safety Population: The safety population will include all patients enrolled who received at least one dose of KZR-616, and will be the population used for the analysis of safety. Adverse event data will be coded to system organ class and preferred term using Medical Dictionary for Regulatory Activities (MedDRA; Version 19.1 or later).

Data will be summarized for the following groups of patients based on the sequence of treatments received in Study KZR-616-003:

Group 1: Arm A (KZR-616:Placebo) from Study KZR-616-003 beginning on Day 1 (first dose of KZR-616) through the end of Study KZR-616-003E

Group 2: Arm B (Placebo:KZR-616) from Study KZR-616-003 beginning on Week 16 (first dose of KZR-616) through the end of Study KZR-616-003E

Groups 1 and 2 combined: from the first dose of KZR-616 in KZR-616-003 through the end of KZR-616-003E

Group 3: Arm B2: Patients receiving KZR-616 from Weeks 16-32 in KZR-616-003 followed by KZR-616 in OLE throughout KZR-616-003E, to evaluate patients who continuously received KZR-616 from KZR-616-003 through KZR-616-003E

Groups 1 and 2 are being assessed for any differences due to the intervening placebo treatment period in Group 1. The rationale for combining Group 1 and Group 2 is to encompass all KZR-616 treatment, and the rationale for assessing Group 3 is to encompass all continuous KZR-616 treatment.

Further details of the statistical methodology, including methods for handling missing data and early withdrawals, will be provided in an SAP that will be finalized prior to database lock. As KZR-616-003E is an open-label extension study, endpoints in addition to those described in [Section 2.2](#) may be conducted as described in the final SAP.

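### The DOI baseline is the start of Study 003 in both arms, but Section 10 starts Arm B at its first KZR-616 dose, so Arm B's DOI can include 16 placebo weeks

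*Combined protocol and SAP*

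**What the plan says.** The Synopsis and Section 2.2.1 give the DOI endpoint in the same words: the proportion improved over time for "patients with baseline core set measures as ascertained at the beginning of KZR-616-003". Neither place separates the arms.

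Section 10 defines its summary groups by treatment sequence in Study 003. The second is "Group 2: Arm B (Placebo:KZR-616) from Study KZR-616-003 beginning on Week 16 (first dose of KZR-616"), running to the end of the extension. The pooled group is "Groups 1 and 2 combined: from the first dose of KZR-616 in KZR-616-003 through the end of KZR-616-003E". The third begins "Group 3: Arm B2: Patients receiving KZR-616 from Weeks 16-32 in KZR-616-003 followed by KZR-616 in OLE". Section 10 explains that pooling is meant to cover all KZR-616 treatment, and Group 3 all continuous KZR-616 treatment.

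Two other statements bear on the reference point. Section 2.2.1 adds, after the endpoint list, "Efficacy endpoints may include treatment periods that include data from Study KZR-616-003 based on treatment sequence in that study", and points to Section 10. Section 3.1 says of the Week 32 Visit of Study 003: "Assessments at this visit performed as part of Study KZR-616-003 will be used as baseline values for the extension study". Section 10 leaves further methods to an SAP to be finalised before database lock, and the document contains no separate SAP text.

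**The concern.** For Arm A, the beginning of Study 003 is the first KZR-616 dose. For Arm B it is the first placebo dose, 16 weeks before any KZR-616. If the endpoint is programmed as worded, an Arm B patient can already meet DOI at Week 16, when the Group 2 window opens and no drug has been given. If that patient then stays level, he or she is a responder at every extension visit.

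What is at stake is how a descriptive proportion is read. The study has no control arm, so nothing within the extension would show how much of the Arm B, Group 3 or pooled DOI rate was already present before KZR-616. No test, alpha level or sample size depends on it.

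**Working it through.** The plan states no figure that could be reproduced here. The check sets the texts side by side, adds timeline arithmetic, and ends with an illustration on assumed rates.

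**1. Candidate reference points for DOI in Arm B**

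| Source | Reference point | Pre-drug placebo weeks included |
|---|---|---|
| DOI endpoint, Synopsis and Section 2.2.1 | Beginning of Study 003 | 16 |
| Section 10, Group 2, Group 3 and pooled | First KZR-616 dose, Week 16 | 0 |
| Section 3.1, extension baseline | Week 32 of Study 003 | 0 |

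No text says which of these applies to DOI in Arm B. Only the first stands in the endpoint itself.

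**2. Placebo share of Arm B's DOI interval under the literal wording**

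Inputs:
- 16 placebo weeks (Section 10).
- 32 weeks of Study 003, taken as nominal.
- A gap of 0 to 8 weeks before the first extension dose (Section 6.1).
- Elapsed extension weeks from the visit days in Table 1, as (day − 1)/7. The ±14-day windows are ignored.

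Share = 16 / (32 + gap + elapsed weeks).

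| Extension visit | Elapsed weeks | Gap 0 | Gap 8 |
|---|---|---|---|
| Week 12 (Day 78) | 77/7 = 11 | 16/43 = 37.2% | 16/51 = 31.4% |
| Week 48 (Day 330) | 329/7 = 47 | 16/79 = 20.3% | 16/87 = 18.4% |
| Week 96 (Day 666) | 665/7 = 95 | 16/127 = 12.6% | 16/135 = 11.9% |

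With a Week 16 baseline the share is 0% at every visit.

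**3. Illustration of the effect on the rate**

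Let p be the Arm B DOI rate counted from Week 16, and q the proportion meeting DOI through placebo-period change alone and keeping it. Both are assumed, and assumed independent. The literal rate is 1 − (1 − p)(1 − q), so the rise is q(1 − p).

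- Lowest: p = 0.50, q = 0.10 gives 0.10 × 0.50 = 5 points.
- Highest: p = 0.30, q = 0.40 gives 0.40 × 0.70 = 28 points.

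If Arm B supplied 12 of 24 patients (also assumed), the pooled rate would rise by half of this, 2.5 to 14 points.

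**4. The two arms at an extension visit**

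Counted from Study 003 Day 1, both arms bring 16 KZR-616 weeks and 16 placebo weeks into the extension, in opposite order. Counted from the first KZR-616 dose, Arm A brings 32 weeks (16 on placebo) and Arm B brings 16 (none on placebo). At extension Week 12 with no gap, that is 43 weeks in Arm A against 43 − 16 = 27 in Arm B.

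**The case against.** The best reply is that the wording is not a settled rule. It can be read as naming which patients are counted, and Sections 1.5 and 2.2.1 both refer to treatment periods and point to Section 10. Some of this stands: the text is not fully unambiguous, and the SAP could still settle it. But as a filter the phrase would remove almost nobody, since inclusion criterion 1 requires completion of Study 003 through Week 32. Neighbouring endpoints name the extension's baseline when they mean it. The pointers to Section 10 are permissive, and that section sets data periods without resetting the DOI baseline.

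A second reply is that status since study entry is a legitimate description in an uncontrolled study. It is, and that version should be kept. It does not, however, serve groups defined to describe KZR-616 treatment.

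Two stronger readings are tempting:

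- A reader might infer that Groups 1 and 2 cannot be compared on DOI because only Group 2 counts placebo time. That does not hold at extension visits, where both intervals contain 16 placebo weeks. The asymmetry exists only when each window opens: DOI is zero by construction in Group 1 and need not be in Group 2.
- A reader might take the whole placebo-period responder share as inflation, up to 40 points in Arm B or 20 points pooled. That assumes none of those patients would also meet DOI from Week 16, and the documents do not support it.

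**Conclusion.** The point holds as a mismatch between the DOI baseline in the endpoint and the start of the Section 10 groups. Followed literally, it lets placebo-period change enter Arm B's DOI, and with it Group 3 and the pooled group. The placebo share of the interval follows from the protocol's own timeline. The 5 to 28 points do not: they rest on assumed rates, on persistence and on independence.

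Upward is the likely direction but not a certain one, because a patient who worsened on placebo and then recovered could meet DOI from Week 16 and not from Day 1. The documents do not support calling this a proven overstatement of drug effect. Because the analysis is descriptive, the consequence is limited to interpretation. It is still more than a missing detail, because the stated baseline works against the stated purpose of the groups.

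**What to change.** For the Section 10 groups, define the DOI baseline as the last core set measures before the patient's first KZR-616 dose: Study 003 Day 1 for Arm A and Week 16 for Arm B. Keep the version from Study 003 Day 1 as a supportive table, labelled as counted since study entry and including placebo time, and show Arm B's DOI at Week 16 beside it.

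This depends on Week 16 core set data being available. Section 1.5 suggests they are ("Mean change from start to end of KZR-616 treatment was the primary efficacy endpoint for Study KZR-616-003"), but the Study 003 assessment schedule is not in the document and should be checked. If they exist, the cost is endpoint or SAP wording and one table, with no new data collection.

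The plan should state three downsides:

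- Arm B and pooled DOI rates may be lower.
- Arm B patients who improved on placebo have less room to meet DOI from Week 16, so Arm B could be understated.
- At extension visits the arms will differ in elapsed time and placebo content, since Arm A's interval still contains its intervening placebo period. Between-group DOI comparisons need that caveat.
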